### **3.5.3     *Control Subjects***

In addition to the 50 primary participants described above, we will seek to enroll 50 healthy control participants. We will attempt to enroll one control subject from each enrolled primary participant's home, preferably a spouse or partner of similar age if possible. We plan to use this data to compare the control participants to the ALS participants at baseline, week 4 and month 6. We will not conduct further follow-up or collect additional samples with the control subjects. There are no specific inclusion or exclusion criteria for control subjects except living in the same household and free of any neurodegenerative disease. This is an observational only study for the control subjects that constitutes minimal risk for the control subjects.

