#### **4.1.6 Microbiome Analyses**

We will compare saliva and stool microbiome samples between patients with ALS and healthy controls at every sampling point. We will compare the changes in the saliva and stool microbiome over time in patients with ALS on Theracurmin to the changes observed in untreated healthy controls. We will compare the enrollment saliva and stool microbiome across patients with different ALS origins (sporadic versus familial), onset regions (limb versus bulbar) and ALSFRS-R progression rates.

Raw, 16S microbiome sequencing data will undergo processing & strict quality control using the Qiime2 pipeline (31). Dada2 (32) will be used to infer and quantify amplicon sequence variants (ASVs). Taxonomy information will be assigned to the ASVs using the q2-feature-classifier (33) against the SILVA 132 database (34). Initial analyses of the data will focus on associations between the diversity of the microflora environment to ALS patients relative to the control samples as well as between the different forms of ALS. We will employ four different metrics for calculating within-sample diversity (alpha diversities: Faith's phylogenetic diversity, Shannon index, Pielou's evenness, and the total number of ASVs) and four different metrics for calculating between-sample diversities (beta diversities: Bray-Curtis dissimilarity, Jaccard dissimilarity, UniFrac, and weighted UniFrac). To identify associations between alpha diversity metrics and ALS, we will employ linear mixed-effects models with household as a random effect. Beta diversity indices will also be evaluated using mixed-effect modeling using the *vegan* package from the R statistical programming environment. The *PhyloSeq* (35) package will be employed to test for differential abundance of individual taxa between ALS patients and the control samples. In brief, raw ASV counts will be agglomerated in Family, Genus, and Species level data before being normalized by the 'poscounts' function from DESeq2 (36). Negative binomial linear models will then be used to identify differential abundance of microflora at the varied taxonomic ranks. Performing all analyses in a linear model framework will allow us to control for potential cofactors such as patient antibiotics usage, age, and gender. The false discovery rate will be used to control for multiple hypothesis testing.

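### The taxa-level negative binomial test is stated without a household term, so as written it does not use the same-home pairing and gives up power

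*Combined protocol and SAP*

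**What the plan says.** Section 3.5.3 builds 1:1 pairing into the control group. It states "We will attempt to enroll one control subject from each enrolled primary" participant's home, and "There are no specific inclusion or exclusion criteria for control subjects except living in the same household and free of any neurodegenerative disease". The target is 50 controls alongside the 50 ALS participants.

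Section 4.1.6 then describes three kinds of ALS-versus-control analysis in one paragraph:

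- Alpha diversity: "we will employ linear mixed-effects models with household as a random effect".
- Beta diversity: "Beta diversity indices will also be evaluated using mixed-effect modeling using the" vegan package in R. The random effect is not named.
- Individual taxa: PhyloSeq is used to "test for differential abundance of individual taxa between ALS patients and the control samples", and after agglomeration and normalisation, "Negative binomial linear models will then be used to identify differential abundance of microflora at the varied taxonomic ranks".

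The paragraph adds that the linear-model framework allows the analysts to "control for potential cofactors such as patient antibiotics usage, age, and gender". Household is not among the examples. No other section supplies a household, pair or participant term for the taxa step. Section 4.1.6 also plans the group comparison at each sampling point, and a comparison of change over time between treated patients and untreated controls.

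**The concern.** People who share a home share diet and environment, so the abundance of a taxon may be correlated within a pair. That is the usual reason for recruiting controls from the same home. A model without household treats the two members of a pair as independent and leaves between-home variation in the noise against which the ALS effect is judged.

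The taxa step has the most tests, across three taxonomic ranks under false discovery rate control, and at most 50 pairs, so lost precision costs detections. It bears on the secondary hypothesis that the fecal microbiome in ALS differs from that of matched controls. Each person also gives up to three samples, so the same silence leaves open how repeat samples enter the model.

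**Working it through.** **Inputs.** The number of pairs is 50, from Section 3.5.3, if every home supplies a control. The documents give no household correlation, mean count, dispersion, fold change or power for the microbiome analyses, so there is no stated figure to reproduce. (The sample size in Section 4.1.2 is for the ALSFRS-R t-test.) All other inputs below are assumptions.

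**Step 1. What the three models use.**

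| Analysis | Model stated | Household |
|---|---|---|
| Alpha diversity | Linear mixed-effects | Random effect, named |
| Beta diversity | Mixed-effect | Random effect not named |
| Individual taxa | Negative binomial linear | No term named |

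**Step 2. Benchmark for normal means, one visit.** Take n pairs, variance s² and within-pair correlation ρ. The true variance of the group difference is 2s²(1−ρ)/n. A model without household reports 2s²/n. The ratio of reported to true standard error is 1/√(1−ρ): 1.05 at ρ = 0.1, 1.12 at 0.2 and 1.20 at 0.3. For normal means, the unpaired standard error is therefore too wide.

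**Step 3. Does that carry over to negative binomial counts?** Two ways of generating 50 pairs were simulated (one visit, assumed mean 100), each analysed with a plain negative binomial model.

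- Exact negative binomial margins, dispersion 1, Gaussian-copula household correlation of 0.2, 0.3 or 0.5: reported/true standard error 1.10, 1.17 and 1.29. Null rejection was 2.7%, 2.2% and 1.2% at nominal 5%.
- Negative binomial with a normal household intercept on the log scale: reported/true standard error 0.82 to 1.03. Null rejection was 5% to 10%.

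In the second case household variation makes the margins heavier-tailed than a negative binomial, which offsets or reverses the effect in Step 2. The direction of the standard-error bias depends on the distribution.

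**Step 4. Power.** For the household-intercept data:

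| Log-scale within-pair correlation | Plain model | With household random intercept | Gain (points) |
|---|---|---|---|
| about 0.17 | 62% | 66% | 4 |
| about 0.24 | 57% | 64% | 7 |
| about 0.32 | 85% | 92% | 7 |
| about 0.43 | 78% | 91% | 13 |

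The power level differs between rows because the assumed settings differ, so compare within rows. A repeat with dispersion 1 (first two rows) or 0.5 (last two) and a log fold change of 0.5 gave powers within 3 points of these. In that repeat the mixed model's null rejection was 5% to 6%.

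The copula data (log fold change 0.55), with household-clustered standard errors in place of a random intercept, show the same pattern:

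- correlation 0.1: 81.7% with and without household;
- correlation 0.2: 77.5% to 81.5%;
- correlation 0.3: 82.0% to 86.8%;
- correlation 0.5: 82.3% to 94.2%.

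Power is lost under both mechanisms, and the loss vanishes as the correlation approaches zero.

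**Step 5. Repeat samples pooled without a participant term.** With T visits, within-person correlation w and household correlation ρ, the normal-means ratio is 1/√(1 + (T−1)w − Tρ). For T = 3, w = 0.6 and ρ = 0.2 it is 1/√(1 + 1.2 − 0.6) = 1/√1.6 = 0.79. The copula simulation at these values gave 0.73, with 15% null rejection. At ρ = 0.3 it gave 0.85 and 9.5%. Only at ρ = 0.5 did the ratio pass 1 (1.09).

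**Step 6. Household as a fixed block.** This spends about 50 parameters on 100 counts, and plain maximum likelihood then underestimates dispersion. In simulation (dispersion 1, mean 100) null rejection was 23% to 28% at nominal 5%, against 5% to 6% with no household term.

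**The case against.** The strongest objection is that the plan is silent here and does not exclude household. The taxa step is introduced as a short summary, the cofactor list is open-ended, and the same paragraph already uses household for alpha diversity. This stands in part: the term is unstated, not ruled out. But the paragraph names mixed models for two analyses and a plain model for the third, in enough detail to name the normalisation function. An analyst following it literally would leave household out.

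A reader might infer more: that the plain model's standard errors are too wide, so any error is safely conservative. The documents do not support that. It follows from the normal-means formula, but negative binomial counts with a household effect gave ratios on both sides of 1 (Step 3), and pooled visits can push the error the other way (Step 5).

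A reader might also take the variance ratio at ρ = 0.3, 1/(1−0.3) = 1.43, to mean that 43% more pairs are needed to recover the lost power. Under the same normal-means formula the figure is ((1.96/√0.7 + 0.842)/2.80)² = (3.185/2.80)² = 1.29, or 29% more. Neither number is a property of this trial, because ρ is not given.

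Three limits stand in full. The size rests on assumed correlations. Section 3.5.3 only attempts to find a control in each home, so there may be fewer than 50 pairs. And the analysis is secondary, in an open-label pilot; household does not matter for comparisons among ALS patients alone.

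**Conclusion.** The point holds as an efficiency loss and a specification gap. As written, the taxa-level model does not use the pairing that the design creates. For assumed log-scale within-pair correlations of about 0.2 to 0.4, 50 complete pairs and one visit, the simulated cost is about 4 to 13 points of power per taxon at nominal 5%, before false discovery rate adjustment. Near zero correlation it is negligible. Whether the plain model's standard errors are too wide or too narrow cannot be settled from the documents, except that pooling visits without a participant term would probably make them too narrow. The primary ALSFRS-R analysis is unaffected. This is a cheap improvement.

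**What to change.** In Section 4.1.6, state the taxa-level ALS-versus-control model as a negative binomial mixed model with household as a random intercept, matching the alpha-diversity model. Add a participant random effect whenever visits are combined or change over time is compared. Keep age, gender and antibiotic use as covariates. Name the random effects for beta diversity too. A random intercept keeps participants whose home supplies no control in the model.

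Do not enter household as an unadjusted fixed block, for the reason in Step 6.

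The cost is a few sentences of SAP text and slightly more model fitting, with no new data. The main downside is possible non-convergence for sparse taxa, so name a fallback in advance. One option is the plain negative binomial model with household-clustered standard errors, which rejected a true null in about 5% of simulated one-visit runs. Also confirm that the chosen software fits random effects.

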**Table 2: Schedule of Events for Control Participants**

	Screening/Enrollment	Wk 4 and Month 6
Consent	R	
Inclusion and Exclusion Criteria Review	R	
Microbiome sample collections by participant at-home	C	C

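### Antibiotic use is a named cofactor for the microbiome models, but the documents give no source for it in the household controls, so an antibiotic-adjusted ALS-versus-control comparison cannot be made from the scheduled data

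*Combined protocol and SAP*

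**What the plan says.** The analysis is in Section 4.1.6 of the combined protocol and SAP. On the group comparison it states: "We will compare saliva and stool microbiome samples between patients with ALS and healthy controls at every sampling point". It also plans to set change over time in treated ALS participants against change in the controls. For alpha diversity, "we will employ linear mixed-effects models with household as a random effect". On covariates, it says that "Performing all analyses in a linear model framework" will "allow us to control for potential cofactors such as patient antibiotics usage, age, and gender".

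The control data are described in two places. Table 2 (Section 3.4.6) has three rows: consent, review of criteria, and at-home microbiome samples at enrollment, week 4 and month 6. Section 3.5.3 says: "There are no specific inclusion or exclusion criteria for control subjects except living in the same household and free of any neurodegenerative disease". It prefers a spouse or partner of similar age, and after listing the three timepoints adds: "We will not conduct further follow-up or collect additional samples with the control subjects".

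For ALS participants, Table 1 and Sections 3.4 and 3.4.3 have concomitant medications entered at the PLM visits, and Section 2.7 describes PLM demographic fields for members with ALS.

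**The concern.** The ALS-versus-control difference is secondary hypothesis 3 in Section 1.2. For hypothesis 2, whether Theracurmin alters the microbiome, the controls are the only untreated reference for change over time, because the trial has no untreated ALS group giving samples. Section 4.1.6 itself names antibiotic use as a potential cofactor in these analyses, yet the schedule obtains it on one side of the comparison only.

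Antibiotic use differs between two people in the same home and changes between samples. It therefore has to be recorded per person and per sampling point, and a course taken shortly before a sample is hard to recover reliably months later. If antibiotic use differs between groups, an unadjusted comparison mixes that difference with the ALS difference, and the scheduled data offer no way to separate them.

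**Working it through.** The plan states no figure on this point, so there is none to reproduce. The check sets the schedules side by side and then asks what a model could estimate from the scheduled data.

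**1. Source of each covariate**

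| Covariate | ALS participants | Controls |
|---|---|---|
| Antibiotic use | Concomitant medications at PLM visits (Table 1; Sections 3.4, 3.4.3) | None stated |
| Age, gender | PLM demographic fields (Section 2.7); no row in Table 1 | None stated; could be asked at the consent contact |

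The control criteria review needs only household and neurodegenerative disease status, so it does not call for antibiotic use. Even if asked at enrollment, one contact could not cover the periods before the week 4 and month 6 samples. The identifier in Section 5.2.2 is described for patients and does not store its inputs, so it supplies nothing here.

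The ALS side also has a gap. Table 1, as it can be read, starts the concomitant medication entry at weeks 1 to 3, and Section 3.4.1 only says participants are taught to enter medications at enrollment. Antibiotic use before the enrollment sample is thus not clearly recorded for them either.

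**2. Extent.** 50 controls sought × 3 sampling points = 150 control samples per body site, if all enroll and return every kit.

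**3. What can be estimated.** Take one sampling point with 50 ALS participants and 50 controls.
- Unadjusted model (intercept, group): 2 columns, rank 2. It can be fitted.
- Model with antibiotics known only in ALS participants: the complete cases are 50 ALS and 0 controls. The group column then equals the intercept, giving rank 2 for 3 columns. The adjusted group effect cannot be estimated.

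**4. Would treating controls as non-users repair it?** Let the true ALS effect be 0, the antibiotic effect be b, and the proportions using antibiotics be p_A (ALS) and p_C (controls). With controls coded as non-users, the group coefficient compares ALS non-users (mean 0) with all controls (mean b·p_C), so its expected value is −b·p_C. Without adjustment it is b·(p_A − p_C). The documents give neither b nor the usage rates. The values below are assumptions: b = −1 SD and the rates shown, with 3,000 simulated data sets per row and 50 per group.

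| p_A | p_C | Unadjusted | Controls coded as non-users | Recorded in both groups |
|---|---|---|---|---|
| 0.10 | 0.10 | −0.010 | 0.090 | −0.011 |
| 0.20 | 0.20 | −0.007 | 0.193 | −0.004 |
| 0.30 | 0.10 | −0.198 | 0.104 | 0.003 |
| 0.20 | 0.05 | −0.151 | 0.049 | −0.002 |
| 0.10 | 0.20 | 0.093 | 0.193 | −0.004 |

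Entries are mean estimated group differences in SD units, where the truth is 0. They match the formulas to about 0.01 SD; in the third row, for example, −b·p_C = 0.10 and b·(p_A − p_C) = −0.20. Coding controls as non-users gives a spurious difference of about 0.05 to 0.19 SD, and where usage is equal it is worse than not adjusting. Recording antibiotics in both groups brings the estimate within about 0.01 SD of 0.

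**The case against.** The strongest reply is that Section 4.1.6 is permissive. It describes what the framework makes possible and gives examples of potential cofactors; it does not fix a covariate set. The only model term it specifies besides the comparison itself is the household random effect for alpha diversity. A reader might infer that the ALS-versus-control analysis cannot be run at all, or that every control would drop out. The documents do not support that: the unadjusted model has full rank, the within-ALS comparisons need no control data, and nothing says that a complete-case analysis will be used or that controls will be coded as non-users. Steps 3 and 4 show what would follow from those choices, not what the plan prescribes.

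The wording may also mean antibiotic use in ALS patients only, since the text generally keeps the word patient for them. That reading is possible, but the sentence covers all the analyses, and the covariate would still be undefined for controls in the group comparison.

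On age and gender the objection largely stands. Table 1 has no demographics row for ALS participants either, so the schedules are not full data lists. The case report form fields (Section 5.2.1) are not shown, staff contact every control for consent, and the preference for a partner of similar age gives a reason to ask. It would go too far to say that these two items will be missing.

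The household random effect does not replace the antibiotic record. It absorbs what a pair shares, not one member's antibiotic course before one sample.

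**Conclusion.** The point holds for antibiotic use. On the scheduled data, an antibiotic-adjusted ALS-versus-control comparison cannot be made at any of the three sampling points, and the same applies to the comparison of change over time with controls. Up to 150 control samples per body site are affected, assuming the target of 50 controls is met and all kits come back. Age and gender are a lesser gap that one question at enrollment would close.

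The primary ALSFRS-R analysis, safety, the unadjusted household mixed models and the within-ALS microbiome analyses are unaffected. The size of any resulting bias is unknown: the 0.05 to 0.19 SD range rests on an assumed antibiotic effect and assumed usage rates, and applies only if controls were coded as non-users. The conclusion itself rests on the absence of any stated source for control antibiotic use; an existing control form that records it at each sample would remove the problem.

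**What to change.** Add one row to Table 2: a short form returned with each control kit at enrollment, week 4 and month 6. It records antibiotic use over a stated look-back window, the same at every timepoint, with age and gender asked once at enrollment. A fixed window is needed because asking about use since the previous sample has no meaning at enrollment.

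Record antibiotic use over the same window for ALS participants at each sample, and make the enrollment entry explicit in Table 1. State in Section 4.1.6 that these fields supply the adjustment.

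The form may also ask controls about curcumin or turmeric products, as a descriptive check that they are untreated. Section 4.1.6 does not name this as a covariate, and it should not be treated as one.

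The cost is a minor amendment, a one-page form in kits that are already sent, and a small burden on controls. No extra visit or staff is needed, and the form does not conflict with the statement in Section 3.5.3 that there is no further follow-up, because it travels with samples already planned. It should be in place before the first samples are collected.

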## 5 SAFETY AND ADVERSE EVENTS

### 5.1 Adverse Events Monitoring

All adverse events (AEs), whether observed by the Investigator, elicited from the participant or volunteered by the participant, and whether ascribed to the drug or not, will be recorded. This will include the following: a brief description of the event, the date of onset, the date of resolution, the duration and type of the event, the severity, contributing factors and any action taken with respect to the study drug. This recording will commence with the institution of protocol-specific procedures (including any pretreatment procedures) and continue at each study visit or telephone contact until 4 weeks following the last study related visit.

For each adverse event, the relationship to the study drug will be recorded as one of the choices on the following scale:

**DEFINITE** Causal relationship is certain (i.e., the temporal relationship between drug exposure and the adverse event onset/course is reasonable, there is a clinically compatible response to de-challenge, other causes have been eliminated and the event must be definitive pharmacologically or phenomenologically using a satisfactory re-challenge procedure if necessary).

**PROBABLE** High degree of certainty for causal relationship (i.e., the temporal relationship between drug exposure and the adverse event onset/course is reasonable, there is a clinically compatible response to de-challenge [re-challenge is not required] and other causes have been eliminated or are unlikely).

**POSSIBLE** Causal relationship is uncertain (i.e., the temporal relationship between drug exposure and the adverse event onset/course is reasonable or unknown, de-challenge/re-challenge information is either unknown or equivocal and while other potential causes may or may not exist, a causal relationship to the study drug does not appear probable).

**UNLIKELY** Not reasonably related, although a causal relationship cannot be ruled out (i.e., while the temporal relationship between drug exposure and the adverse event onset/course does not preclude causality, there is a clear alternate cause that is more likely to have caused the adverse event than the study drug).

**NOT RELATED** No possible relationship (i.e., the temporal relationship between drug exposure and the adverse event onset/course is unreasonable or incompatible, or a causal relationship to study drug is implausible).

The severity of each adverse event must be recorded as one of the choices on the following scale:

**MILD** No limitation of usual activities

**MODERATE** Some limitation of usual activities

**SEVERE** Inability to carry out usual activities

The expectedness of an AE must be indicated when reporting adverse events. An unexpected adverse event is any adverse experience for which the specificity or severity of the event is not consistent with the known side effects of Theracurmin (or similar curcumin products), as described in section 3.9 above.

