### **3.3.4 Safety and Tolerability in Patients with ALS**

We will record adverse and serious adverse events throughout the study. The PI will determine whether these are related to treatment. Patients will also measure and record their side effects at Month 0-6 Internet Visits on their PLM profile (See Appendix C).

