## **3.4 Study Schedule**

Following informed consent and screening, enrollment visit activities will commence and Therarcurmin treatment will be started. Treatment and all study activities will end at month 6. Participants will be required to make 4 video/telephone visits with the Duke study team (enrollment, weeks 1, 2, and 3). Participants will not be required to make any physical visits to Duke. At months 2-6, participants will make “Internet PLM visits” by measuring their own ALSFRS-R score and weight and height, and logging onto the PLM website to record it as well as perceived efficacy, perceived side effects, perceived compliance, changes in concomitant medications and Thrive questionnaires. Participants will be reminded to log into their PLM profile and record the above-mentioned data points via email and text reminders from PLM. The study coordinator will call/video participants at enrollment, weeks, 1, 2, 3 and for training and any time afterward when participants have not entered data for 2 weeks beyond expected entries. The call script for such communications can be found in Appendix I.

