**Table 1: Schedule of Events for Primary Participants**

	Enrollment*	Wk 1,2,3	Wk 4	Mos 2-5	Mo 6**
Inclusion and exclusion criteria review	R				
Consent	R				
Participant registers account on PLM	R				
Phone/video visits with participant to record ALSFRS-R and teach/troubleshoot as necessary	R	R			
		P	P	P	P
PLM virtual visits by participant to record ALSFRS-R, anthropometrics, treatment self-evaluation, Con Meds, and AE					
Long Thrive Evaluation	P		P		P
Short Thrive Evaluation		P		P	
Microbiome sample collections by participant at-home	P		P		P

\*intervention begins

\*\*intervention ends

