### **5.1.1 *Reporting of Serious Adverse Events***

A serious adverse drug event (SAE) is defined as any adverse event that occurs during the study that results in any of the following outcomes: death, a life- threatening adverse event (i.e., the participant was at immediate risk of death from the event as it occurred; does not include an event, that had it occurred in a more severe form, might have caused death), inpatient hospitalization or prolongation of existing hospitalization (hospitalizations scheduled before enrollment for an elective procedure or treatment of a pre-existing condition which has not worsened during participation in the study will not be considered a serious adverse event), a persistent or significant disability/incapacity (substantial disruption of one's ability to conduct normal life functions), a congenital anomaly/birth defect, a medically important event or required medical intervention to avoid one of the above outcomes. In addition to the above procedures for AEs, all SAEs will be reported to the IRB within 24 hours of recording. All serious adverse event information will be followed until resolution or an appropriate end point is reached. This may involve contacting other clinicians responsible for the participant's care to obtain information on diagnoses, investigations performed and treatment given

Fatal or life-threatening, unexpected adverse events will be reported to the FDA by telephone, facsimile, or in writing as soon as possible, but no later than 7 calendar days after first knowledge by the Sponsor-investigator. Serious, unexpected adverse events that are not fatal or

life-threatening will be reported to the FDA by telephone, facsimile, or in writing as soon as possible, but no later than 15 calendar days after first knowledge by the sponsor-investigator.

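### The adverse event window runs to 4 weeks after the last visit, but no visit, call or PLM entry is scheduled in those 4 weeks

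*Combined protocol and SAP*

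**What the plan says.** Section 5.1 (Adverse Events Monitoring) starts AE recording with the first protocol-specific procedure and has it "continue at each study visit or telephone contact until 4 weeks following the last study related visit". It covers all events, "whether observed by the Investigator, elicited from the participant or volunteered by the participant". For each event it asks for, among other items, "the date of onset, the date of resolution, the duration and type of the event". Its Definite and Probable causality grades both require that "there is a clinically compatible response to de-challenge".

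The schedule stops earlier. Section 3.4 states: "Treatment and all study activities will end at month 6". The required staff video or telephone visits are at enrollment and weeks 1, 2 and 3. The Table 1 row "PLM virtual visits by participant to record ALSFRS-R, anthropometrics, treatment self-evaluation, Con Meds, and AE" has its last entry under Mo 6, which a footnote marks as the end of the intervention. Section 3.3.4 says: "Patients will also measure and record their side effects at Month 0-6 Internet Visits on their PLM profile".

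For SAEs, section 5.1.1 adds: "All serious adverse event information will be followed until resolution or an appropriate end point is reached". No equivalent is stated for non-serious AEs. Section 5.2 says that there is no data and safety monitoring board (DSMB), no formal safety monitoring plan and no formal stopping rule.

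**The concern.** The plan promises four weeks of recording at visits or calls and then schedules neither. Those weeks begin when the study supply ends. What happens to an open event once the product is withdrawn is informative for both its outcome and its attribution.

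Three things are at stake. First, new AEs and SAEs in the tail depend on someone reporting them unprompted. The IRB reporting clock in section 5.1.1 starts at recording, and the FDA clock at the sponsor-investigator's first knowledge, so an SAE that nobody hears about starts neither. Second, a non-serious AE still present at month 6 may never get a resolution date. Third, section 3.2.2 lets participants buy the product once the study ends. Unless they are asked, it is not known whether withdrawal took place at all.

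With no DSMB or formal safety monitoring plan, routine AE capture carries the safety assessment, which section 3.3.4 lists among the outcome measures.

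**Working it through.** The plan gives no figure to reproduce here. The check sets the window beside the contacts, then sizes the gap.

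**Scheduled contacts after month 6**

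| Type of contact | Last scheduled | In the following 4 weeks |
|---|---|---|
| Staff video/telephone visit (3.4, Table 1) | Week 3 | 0 |
| PLM entry with AEs or side effects (3.3.4, 3.4.3, Table 1) | Month 6 | 0 |
| Physical visit (3.4) | none required | 0 |

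**Which visit anchors the window.** If only staff video/telephone visits counted, the last would be week 3 and recording would stop at week 3 + 4 = week 7. That contradicts section 3.3.4, which has AEs recorded throughout the study, and Table 1, which has AE entries to month 6. Month 6 is the sensible anchor for a participant who completes.

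**Size of the gap**

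- Assumption: 6 months = 183 days. Window = 183 + 28 = 211 days.
- Share without scheduled collection = 28 / 211 = 13.3%.
- Range: 28 / (184 + 28) = 13.2% to 28 / (180 + 28) = 13.5%.
- Person-time: 50 participants (section 3.5) x 28 days = 1,400 person-days; 1,400 / 365.25 = 3.8 person-years. This is an upper limit, since deaths shorten it. Early stoppers are not removed, because they too have a last visit and a 4-week tail.

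**Whether the reminder call fills the gap.** Section 3.4.3 has a coordinator call at 7 + 7 = 14 days after an overdue entry.

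- If the participant then enters Month 6 data, that entry becomes the last visit and a full 28 days follow with nothing scheduled.
- If the participant never enters, the last visit is Month 5. With entries every 30 days (section 3.3.1), the window closes 30 - 28 = 2 days before the Month 6 due date, ahead of the call.

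In neither case does the call fall in the 4-week tail.

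**Effect on the causality grade.** Definite and Probable need a compatible de-challenge response. Possible allows that information to be unknown. Section 3.2.3 provides for dose reduction or stopping for AEs and one holiday of up to 7 days, all documented, so de-challenge evidence may already exist before month 6. What remains is the non-serious AE that is open at month 6 in a participant whose dosing was never interrupted. If nobody asks afterwards, it can be graded no higher than Possible.

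**The case against.** The best defence is that section 5.1 defines a reporting window and does not itself promise a call. It counts observed, elicited and volunteered events alike. Section 3.9 gives participants staff contact numbers and round-the-clock emergency cover. Sections 3.5 and 3.6 draw participants mainly from the investigator's own clinic, so many may be seen in ordinary care. Known SAEs are followed to resolution.

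The stakes are also low. Section 3.9 puts side effects below 10%, mostly gastrointestinal. That is fewer than about 50 x 0.10 = 5 people with product side effects at any time, and fewer still with one open at month 6, though background ALS events would be more common. Section 4 plans no AE analysis and no hypothesis concerns safety.

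Most of this stands and limits the weight of the point. It does not close the gap: each route depends on the participant or a clinician raising the event, and none asks everyone.

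A reader might infer more than the documents support:

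- **That no AE can be recorded after month 6.** It can, if volunteered, observed, or part of follow-up of a known SAE.
- **That the causality scale fails for events open at month 6.** It does not. The Possible grade accepts unknown de-challenge, and interruptions under section 3.2.3 may already have supplied the evidence.
- **That the efficacy result is affected.** Nothing here touches the ALSFRS-R comparison or the sample size.

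**Conclusion.** The point holds as an inconsistency between section 5.1 and the schedule, with a limited safety consequence. For a participant who completes, 28 of about 211 days (13%) of the stated window have no scheduled AE collection, up to 1,400 person-days in all. The effect is incomplete capture of new AEs and SAEs after the product stops. For non-serious AEs open at month 6, resolution dates may be missing, as may the de-challenge response where dosing was never interrupted.

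No count of missed events is claimed, because the documents give no event rate for this period, and few product-related events are expected. The conclusion rests on month 6 being the last study visit and on 6 months being about 183 days. The timeline figure (3.4.4) and the call script (Appendix I) were not available. A follow-up call shown only there is unlikely, given that section 3.4 ends all activities at month 6.

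The change is worth making because it is cheap and makes the stated window real.

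**What to change.** Add to section 3.4 and Table 1 one coordinator call or PLM entry about 4 weeks after month 6, or after early stopping. It should ask about:

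1. new AEs and SAEs since the last entry;
2. the outcome and resolution date of any AE still open at that entry;
3. whether the participant is still taking the product.

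Amend the sentence in section 3.4 that ends all study activities at month 6, so that it ends treatment then and allows for this contact.

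Shortening the section 5.1 window to month 6 would make the wording consistent but would collect nothing more, so it is the weaker choice.

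Cost: at most 50 short contacts of coordinator time, one more column in Table 1, and one more contact for participants, some of them late in their disease. No new measurement is needed.
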